**Gansu Provincial Maternity and Childcare Hospital
Statistical Analysis Plan (SAP)**

Project name: A cohort study on the effects of gestational blood sugar management and postnatal nurturing environment on delayed language development in children

Project source: National Clinical Medical Research Center for Child Health and Disease

Responsible person: [name]

Department: Research Center

Principal Investigator: [name]

Research period: December 2022 to November 2025

Version number: 1.0.

Date of version: April 20th, 2023

According to the implementation plan of the "Western Baby Plan" queue, 1.5-2.5-year-old offspring children who have entered the "Western Baby Plan" queue as research objects were surveyed. The language development and family nurturing environment of 2-year-old children using the "Language Development Evaluation S-S Method, Gesell Infant and Toddler Development Scale, and 0-6 Year Old Family Nurturing Environment Evaluation Scale" were evaluated. We investigated the results of blood sugar screening during pregnancy of children's mothers using retrospective cohort study methods, and follow up the blood sugar management effect of pregnant women with abnormal blood sugar before delivery. At the same time, pregnant women diagnosed with abnormal blood sugar during pregnancy are used as research objects to conduct prospective cohort studies: collect standardized epidemiological survey data of the "Western Baby Plan" queue (mainly including general conditions, diet, exercise, environmental factor investigations, etc.), follow up blood sugar control methods at 36-40 weeks of pregnancy, record pre-pregnancy blood sugar control results and neonatal outcomes, collect peripheral blood and umbilical blood during delivery and store them in the mother-infant biological sample library. The study would follow up the growth and development of offspring, and evaluate the language development and family nurturing environment of 2-year-old children using the "Language Development Evaluation S-S Method, Gesell Infant and Toddler Development Scale, and 0-6 Year Old Family Nurturing Environment Evaluation Scale".

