Sample size estimation: Referring to delayed language development in children as the disease outcome, the incidence rate (p_1) of delayed language development in the group exposed to high prenatal sugar is 15%, and the relative risk (RR) is 2.0, with a desired significance level (α) of 0.05 and a desired power ($1-\beta$) of 0.90. By plugging in these values into

the formula, it is determined that both the exposed group and the control group require 160 individuals. Considering the possibility of loss to follow-up, the sample size is increased by 10%. The final estimated sample size for the cohort is 356 cases, with a planned investigation of 360 individuals in the blood sugar abnormality specialized disease cohort.

The sample calculation formula for the cohort study collects data information through the electronic medical record system and the Western Children's Health and Disease Cohort Platform, with dual data entry into an Excel database. Differences in the distribution of general conditions of pregnant women are compared using statistical methods such as the chi-square test or Fisher's exact probability test for categorical data (Socio demographic profile, menstrual and reproductive history, indoor environment Environmental factors, Scale indicators etc.), and statistical methods such as the t-test or ANOVA test for continuous data (Check labs (e.g., fasting blood glucose, glycosylated hemoglobin, lipids, liver and kidney function, etc.). After further controlling for confounding factors, logistic regression analysis is used to explore the impact of poor blood sugar management (high prenatal sugar exposure) on delayed language development around 1-2 years of age.

The combined effect of GDM and postnatal environment of the offspring was analyzed using an EXCEL spreadsheet developed by Andersson et al. The additive interaction was evaluated using three indices: relative excess risk due to interaction (RERI), attributable proportion due to interaction (AP), and synergy index (S). If the 95% confidence intervals (CI) of RERI and AP included 0, and the 95% CI of S included 1, it indicated no additive interaction; otherwise, there was an additive interaction.

The regression models were used to screen the effect of maternal GDM and related factors on the delayed language development (DLD) in

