offspring. The binomial logistics regression model and the lasso regression model were constructed by using the "rms" and "glmnet" package to analyse risk factors. The nomogram, which based on proportionally converting each regression coefficient to a zero to one-hundred-point scale, was used to screen the effect of maternal GDM and related factors on the DLD. The effect of the variable with the highest β coefficient was assigned one hundred points. The points were added across independent variables to derive total points, which were converted to predicted probabilities. The total scores of each patient were calculated based on the nomogram for clinical prediction. We used the predictive performance of the nomogram was measured by concordance index (C index). Prediction models were validated by plotting calibration curves and using bootstrap method with one thousand replicate samples. The clinical validity of the prediction model was evaluated using decision curve analysis (DCA).

All analyses were performed using SPSS software (SPSS Inc., Chicago, IL, USA, version 21.0) and R version (4.1.3, <http://www.r-project.org/>). The significance level for statistical tests is set at a value of 0.05, the selection criterion for the regression equation is set at a level of 0.05, and the exclusion level is set at 0.10. Missing values are handled according to the default method in SPSS, which means that observations with missing values in the test variables are excluded from the analysis. A p-value of <0.05 indicates a statistically significant difference.

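### The 0.05-in / 0.10-out selection rule names no model; if it reaches the confounder-adjusted glucose model, it can drop confounders, and the usual CI and p-value ignore the selection

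*Protocol*

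**What the plan says.** The Protocol describes two uses of regression.

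- **Effect model** (statistical methods paragraph after the sample size): "After further controlling for confounding factors, logistic regression analysis is used to explore the impact of poor blood sugar management" on delayed language development. The exposure is high prenatal glucose.
- **Risk-factor and nomogram models** (later paragraph): "The binomial logistics regression model and the lasso regression model were constructed" in R to analyse risk factors and build the nomogram. The lasso is named only here. The bootstrap check is also tied to this use: "Prediction models were validated by plotting calibration curves and using bootstrap method with one thousand replicate samples".

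The selection rule comes after both, in the general closing paragraph. That paragraph opens "All analyses were performed using SPSS software" and also holds the significance level and the missing-data rule. The rule reads: "the selection criterion for the regression equation is set at a level of 0.05, and the exclusion level is set at 0.10". The regression equation is singular and unnamed.

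**The concern.** In an observational cohort the adjusted odds ratio is only as good as the adjustment. An entry test at p<0.05 asks whether a covariate significantly predicts the outcome in this sample. It does not ask whether the covariate confounds the exposure effect. With few events, a real confounder of weak or moderate strength can fail that test and be left out. The final model is then reported with an ordinary confidence interval and p-value, as if its covariates had been fixed beforehand.

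At stake are residual confounding in the glucose odds ratio and a test that rejects too often. The bootstrap does not help, because it is stated for the prediction models and not for the exposure effect. The point is not that a confounder list is absent. It is that a stated rule has no stated limit, so it can reach a model for which it is poorly suited.

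**Working it through.** **Sample size and expected events.** The sample size paragraph gives 15% incidence in the exposed group, RR 2.0, α 0.05, power 0.90 and 160 per group. Sidedness is not stated; two-sided is assumed. The two-proportion formula is

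n = [1.960·√(2p̄(1−p̄)) + 1.282·√(p₁(1−p₁)+p₂(1−p₂))]² / (p₁−p₂)².

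- 30% v 15%: (1.960·√0.34875 + 1.282·√0.3375)² / 0.15² ≈ 161, which matches the stated 160.
- 15% v 7.5%: (1.960·√0.19969 + 1.282·√0.196875)² / 0.075² ≈ 371, which does not match.
- 320/0.9 = 356, as stated.

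Expected events are therefore 160 × (0.15 + 0.30) = 72 if 15% is the unexposed risk, which fits the stated size. They are 160 × (0.15 + 0.075) = 36 if 15% is the exposed risk, as labelled. Both are carried forward.

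**Main simulation.** Logistic models with n = 320 and 8 mutually independent standard-normal covariates. Stepwise selection used score-test entry at p<0.05 and Wald removal at p>0.10, with the exposure always kept. There were 2000 runs per cell (Monte Carlo SE 0.5–0.7 points). Confounder strengths are assumptions, given as log-odds per SD with exposure/outcome.

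Type I error (%), stepwise v all 8 kept, true OR 1.0:

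| Pattern | 36 events | 72 events |
|---|---|---|
| A: 8 at 0.25/0.20 | 10.1 v 5.0 | 11.3 v 5.1 |
| B: 8 at 0.25/0.25 | 10.8 v 5.2 | 11.4 v 5.0 |
| C: 4 at 0.25/0.25, 4 noise | 6.6 v 4.9 | 7.4 v 4.7 |
| D: 8 at 0.15/0.15 | 5.4 v 4.7 | 7.8 v 5.7 |
| E: 8 at 0.25/±0.25 (mixed direction) | 7.1 v 5.2 | 8.0 v 4.8 |
| F: 4 at 0.4/0.3, 4 noise | 10.8 v 5.1 | 10.1 v 4.5 |
| G: 4 at 0.5/0.5, 4 noise | 10.4 v 4.5 | 7.0 v 4.2 |

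- Mean OR, as exp(mean log OR), was 1.00–1.26 with stepwise and 0.99–1.01 with all kept. In pattern E the stepwise mean was 1.00.
- Stepwise kept 13–70% of true confounders at 36 events and 18–90% at 72.
- At a true OR of 2.0, stepwise gave mean OR 2.01–2.62 and coverage 88.6–94.9%. All kept gave 2.05–2.14 and 94.1–96.2%.
- A separate run of pattern B (1000 runs per cell) gave stepwise type I error 10.7/13.2% and mean OR 1.28/1.21 at 36/72 events. All kept gave 4.1/3.8% and about 1.00.

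**Second design.** Four true confounders, six noise covariates, exposed–unexposed imbalance 0.2–0.5 SD, 800 runs per scenario. False rejection was 4.5–14.5% with stepwise and 3.7–6.0% with the true confounders fixed. The largest mean log OR was 0.254, that is exp(0.254) = 1.29. The share of runs omitting a given confounder fell with its strength:

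| Outcome OR per SD | 36 events expected (11.25%) | 72 events expected (22.5%) |
|---|---|---|
| 1.3 | about 70% | about 53% |
| 1.5 | about 42% | about 20% |
| 1.8 | about 15% | about 3% |

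**Correlated covariates.** Pattern B was rerun with pairwise correlation (1000 runs per cell). In one of the two independent runs, total confounding was explicitly held the same (crude OR about 1.52–1.56). Stepwise results at 36/72 events:

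| Correlation | Type I error, run 1 | Type I error, run 2 | Mean OR, run 1 | Mean OR, run 2 |
|---|---|---|---|---|
| 0.3 | 6.4/7.9% | 6.8/7.8% | 1.13/1.09 | 1.12/1.11 |
| 0.5 | 4.1/5.9% | 6.2/6.7% | 1.06/1.06 | 1.08/1.06 |

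With all covariates kept, run 1 gave 4.9/6.4% at 0.3 and 4.2/5.6% at 0.5. Retained covariates partly stand in for omitted ones, so the harm shrinks.

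**The case against.** A reader might infer that the Protocol selects the confounders of the glucose effect by p-value. It does not say so. The rule follows the risk-factor text, which is the only place where regression is described as screening. The opening about all analyses is the subject of the software sentence, not of the selection sentence. For the effect model the text speaks of controlling for confounders, which points away from dropping them. That sentence also comes straight after univariate comparisons of maternal characteristics, so those might be the route by which covariates are chosen. All of this stands, and the finding is therefore conditional on scope.

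A reader might also infer that the odds ratio will be inflated by about a quarter. That does not stand. The largest figures need several independent confounders acting in one direction. The candidate covariates ("Socio demographic profile, menstrual and reproductive history, indoor environment Environmental factors, Scale indicators etc") may well be correlated, and the document gives no correlations. With correlation the bias is much smaller, and at 0.5 one run showed no excess type I error. Mixed directions give no bias in the OR, and strong confounders at the higher event count are mostly kept.

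The comparison with all covariates kept is also generous, since that model contains every true confounder. When only 4 of 8 same-direction independent confounders were fixed, type I error was 4.9–11.8% and mean OR 1.09–1.26 in the main simulation. In the separate run of pattern B they were 8.9/13.5% and 1.28/1.27. A short fixed list is therefore no cure.

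The Protocol's word for the analysis is exploratory. That lowers the stakes, but it does not make the interval or p-value correct.

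**Conclusion.** The scope of the rule is unclear, and one of its two plausible readings harms the adjusted glucose effect. On that reading, with 320 children and 36 to 72 events, weak to moderate confounders can be omitted, and nothing corrects the reported inference.

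The size is a range over assumptions, not an estimate for this study. With independent covariates, type I error was about 5–13% in the main patterns (up to 14.5% in the second design), and a null effect appeared as a mean OR of 1.00 to about 1.28. With same-direction confounders correlated at 0.3–0.5, the figures were about 4–8% and 1.06–1.13. A larger analysed number would retain more confounders and reduce the effect. If the rule was meant only for the nomogram, one sentence settles the matter.

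**What to change.** State three things in the Protocol:

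1. In the effect model, the glucose/GDM exposure is always kept.
2. The full set of plausible measured confounders, not a short list, is named before analysis on subject-matter grounds and kept whatever the p-values. The data are already collected ("mainly including general conditions, diet, exercise, environmental factor investigations, etc", together with sociodemographic and reproductive history).
3. The 0.05/0.10 rule and the lasso apply only to the risk-factor/nomogram model.

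If events per coefficient are low, fit the same set with Firth penalisation rather than trimming it. Exposure plus 8 covariates is 9 coefficients, so 36/9 = 4 or 72/9 = 8 events each. With 12 covariates it is 36/13 = 2.8 or 72/13 = 5.5. In simulation the Firth fit held type I error at 3.9–5.5% (8 covariates) and 3.9–5.3% (12), with mean OR 1.97–2.02 and 1.96–2.02 for a true 2.0. Multi-level categorical variables could take the count beyond 12, which was not tested.

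The cost is wording, no new data, and a small change of fitting method if Firth is used. With 8 covariates the standard error was 2–7% larger than with stepwise (no true effect), so the CI is slightly wider. In the mixed-direction pattern, where stepwise gives no bias in the OR, power at OR 2.0 was 41.5% v 44.5% at 36 events and 63.4% v 64.3% at 72. Part of that difference reflects the inflated type I error of stepwise in the same pattern (7.1–8.0%).
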